4.2 Randomization and Blinding

4.2.1 Randomization Scheme

Randomization will be managed and maintained centrally through an automated Interactive Voice Response System/Interactive Web Response System. Patients will be randomized in a 1:1 ratio to one of the two treatment arms.

Randomization will be stratified according to:

- The number of previous HER2-directed regimens in the metastatic setting ($N = 2$ or $N \geq 3$).
- Geographic region (North America vs. Europe, including Israel vs. RoW)
- Visceral vs. non-visceral only disease
- Estrogen receptor+ (ER+) and/or progesterone receptor (PR+) (i.e., hormone receptor +) versus ER- and PR- (i.e., hormone receptor -).

4.2.2 Enrollment and Randomization of Patients to Treatment

Once eligibility is confirmed, patients will be randomized to a treatment group according to the randomization schedule. All patients must commence treatment with investigational products no later than 14 days after randomization. Patients who do not meet the eligibility criteria will not be randomized in the study, but may be rescreened up to two times at the Investigator's discretion.

4.2.3 Blinding and Breaking the Blind

This is an open-label study.

5 STUDY POPULATION

5.1 Inclusion Criteria

Each patient will be entered into this study only if she/he meets all of the following criteria:

1. Aged ≥ 18 years at signing of informed consent.
2. Histologically confirmed MBC, current stage IV.
3. Documented HER2 overexpression or gene-amplified tumor (immunohistochemistry [IHC] 3+; or IHC 2+ with confirmatory fluorescence in situ hybridization [FISH]+). (Note: Patients who are IHC 0 or 1+ are not eligible to participate in the study). Tumor samples will be evaluated for HER2 expression by IHC (HercepTest™) and if required for gene amplification by FISH analysis (IQFISH pharmDx™).
4. Prior treatment with at least two HER2-directed regimens for metastatic breast cancer. A new regimen is defined as a modification in a planned course of therapy to include other treatment agents (alone or in combination) as a result of disease progression, relapse, or toxicity ([Rajkumar et al., 2011](#)). A new regimen also starts when a planned period of observation off therapy is interrupted by a need for additional treatment for the disease.
5. At least one measurable lesion as defined by Response Evaluation Criteria in Solid Tumors (RECIST v1.1 ([Eisenhauer et al., 2009](#)), see [Appendix 7](#)). Specifically, no ascites, pleural or pericardial effusions, osteoblastic bone metastases, or carcinomatous lymphangitis of the lung as the only lesion are allowed.
6. Left ventricular ejection fraction (LVEF) $\geq 50\%$ measured by multiple-gated acquisition scan (MUGA) or echocardiogram (ECHO).
7. Eastern Cooperative Oncology Group (ECOG) status of 0 to 1 (see [Appendix 3](#)).
8. Negative β -human chorionic gonadotropin (hCG) pregnancy test for premenopausal women of reproductive capacity (those who are biologically capable of having children) and for women less than 12 months after menopause.
9. Women of childbearing potential must agree and commit to the use of a highly effective method of contraception, as determined to be acceptable by the Investigator, from the time of informed consent until 28 days after the last dose of the investigational products. Men must agree and commit to use a barrier method of contraception while on treatment and for 3 months after last dose of investigational products.

10. Provide written, informed consent to participate in the study and follow the study procedures.

5.2 Exclusion Criteria

A patient will be excluded from this study if she/he meets any of the following criteria:

1. Received previous therapy with capecitabine, neratinib, lapatinib, or any other HER2-directed tyrosine kinase inhibitor.
2. Received prior therapy resulting in a cumulative epirubicin dose $>900 \text{ mg/m}^2$ or cumulative doxorubicin dose $>450 \text{ mg/m}^2$. If another anthracycline or more than one anthracycline has been used, the cumulative dose must not exceed the equivalent of 450 mg/m^2 doxorubicin.
3. Any major surgery ≤ 28 days prior to the initiation of investigational products, or received anti-cancer therapy (including chemotherapy, biological therapy, hormonal therapy, investigational agents, or other anti-cancer therapy) administered ≤ 21 days prior to the initiation of investigational products.
4. Received radiation therapy ≤ 14 days prior to initiation of investigational products.
5. Symptomatic or unstable brain metastases. (Note: Asymptomatic patients with metastatic brain disease who have been on a stable dose of corticosteroids for treatment of brain metastases for at least 14 days prior to randomization are eligible to participate in the study).
6. Active uncontrolled cardiac disease, including cardiomyopathy, congestive heart failure (New York Heart Association functional classification of ≥ 2), unstable angina, myocardial infarction within 12 months of enrollment, or ventricular arrhythmia.
7. QTc interval >0.450 seconds or known history of QTc prolongation or Torsades de Pointes.
8. Screening laboratory assessments outside the following limits:

Laboratory endpoint	Required limit for exclusion
Absolute neutrophil count (ANC)	$<1500/\mu\text{L}$ ($<1.5 \times 10^9/\text{L}$)
Platelet count	$<100,000/\mu\text{L}$ ($<100 \times 10^9/\text{L}$)
Hemoglobin (Hb)	$<8 \text{ g/dL}$ (transfusions allowed) Transfusions must be at least 14 days prior to randomization.
Total bilirubin	$>1.5 \times$ institutional upper limit of normal (ULN)
Aspartate aminotransferase (AST) and/or Alanine aminotransferase (ALT)	$>3 \times$ institutional ULN ($>5 \times$ ULN if liver metastases are present)
Creatinine clearance	$<50 \text{ mL/min}$ (as calculated by Cockcroft and Gault formula ^a or Modification of Diet in Renal Disease [MDRD] formula ^b)

^a Cockcroft and Gault, 1976

^b Levey et al., 1999

9. Active infection or unexplained fever $>38.5^{\circ}\text{C}$ (101.3°F).
10. Other malignancy within the past 3 years with the exception of a) adequately treated basal cell carcinoma, squamous cell skin cancer, or thyroid cancer; b) carcinoma in situ of the cervix or vulva; c) prostate cancer of Gleason Score 6 or less with stable prostate-specific antigen levels; or d) cancer considered cured by surgical resection or unlikely to impact survival during the duration of the study, such as localized transitional cell carcinoma of the bladder, or benign tumors of the adrenal or pancreas.
11. Currently breast-feeding.
12. Significant chronic gastrointestinal disorder with diarrhea as a major symptom (e.g., Crohn's disease, malabsorption, or Grade ≥ 2 (NCI CTCAE v.4.0) diarrhea of any etiology at screening).
13. Active infection with hepatitis B or hepatitis C virus.
14. Known dihydropyrimidine dehydrogenase deficiency.
15. Known hypersensitivity to 5-fluorouracil or to any component of the investigational products or compounds of similar chemical composition.
16. Unable or unwilling to swallow tablets.
17. Evidence of significant medical illness, abnormal laboratory finding, or psychiatric illness/social situations that would, in the Investigator's judgment, make the patient inappropriate for this study.

6 INVESTIGATIONAL PRODUCTS AND ADMINISTRATION

6.1 Investigational Product Administration

6.1.1 Neratinib Plus Capecitabine

Neratinib

Neratinib investigational product will be supplied as 40 mg film-coated tablets packaged in bottles with desiccant.

Neratinib (240 mg initial dose; provided as six 40 mg tablets) will be self-administered orally by patients on a daily basis, starting with Cycle 1/Day 1. Neratinib should be taken with food, in the morning.

Neratinib is to be taken continuously in 21-day cycles, with no rest between cycles.

Capecitabine

Capecitabine investigational product is available as 150 mg and 500 mg film-coated tablets.

Capecitabine (total dose of 1500 mg/m² daily, in 2 approximately evenly divided doses) will be self-administered orally by patients, starting with Cycle 1/Day 1. Doses are to be taken daily on Days 1 to 14 of each 21-day cycle. Capecitabine should be taken with water within 30 minutes after a meal.

During treatment with neratinib plus capecitabine, patients should be monitored for conditions that may require dose to be held or discontinued, as described in [Appendix 2](#). Careful attention should be paid to the onset of diarrhea or hand-foot syndrome in particular, and early dose adjustment or prophylactic therapy should be implemented as described in [Appendix 2](#).

Daily dosing of neratinib plus capecitabine should continue until a criterion for treatment withdrawal or study withdrawal is met (see Sections [10.1](#) and [10.2](#), respectively).

6.1.2 Lapatinib Plus Capecitabine

Lapatinib

Lapatinib investigational product is available as 250 mg film-coated tablets.

Lapatinib (1250 mg initial dose; provided as five 250 mg tablets) will be self-administered orally by patients on a daily basis, starting with Cycle 1/Day 1. The total daily dose of lapatinib should be taken 1 hour before or after breakfast; daily doses should not be divided.

Lapatinib is to be taken continuously in 21-day cycles, with no rest between cycles.

Refer to the lapatinib (Tykerb[®]) [US Package Insert](#) and/or the (Tyverb[®]) [SPC](#) for further information on dosing

Capecitabine

Capecitabine investigational product is available as 150 mg and 500 mg film-coated tablets.

Capecitabine (total dose of 2000 mg/m² daily, in 2 approximately evenly divided doses) will be self-administered orally by patients, starting with Cycle 1/Day 1. Doses are to be taken daily on Days 1 to 14 of each 21-day cycle. Capecitabine should be taken with water within 30 minutes after a meal.

During treatment with lapatinib plus capecitabine, patients should be monitored for conditions that may require dose to be held or discontinued, as described in [Appendix 2](#). Careful attention should be paid to the onset of diarrhea or hand-foot syndrome in particular, and early dose adjustment or prophylactic therapy should be implemented as described in [Appendix 2](#).

Daily dosing of lapatinib plus capecitabine should continue until a criterion for treatment withdrawal or study withdrawal is met (see Sections [10.1](#) and [10.2](#), respectively).

Refer to the capecitabine (Xeloda[®]) [US Package Insert](#) and/or the [SPC](#) for further information on dosing.

6.1.3 Dose Adjustment

Investigational product dose adjustment and/or discontinuation should be performed according to [Appendix 2](#) and Section [10.1](#).

Recommended dose reductions for the -1 and -2 dose levels of neratinib are listed in [Table 2](#).

Table 2. Dose Reduction Levels for Neratinib-Related Toxicity

Dose Level	Neratinib
Starting Dose	240 mg
-1	160 mg
-2	120 mg

Recommended dose reductions for the -1 and -2 dose levels of capecitabine in combination with neratinib are listed in [Table 3](#).

Table 3. Dose Reduction Levels for Capecitabine-Related Toxicity (When Administered in Combination with Neratinib)

Dose Level	Capecitabine (administered in combination with neratinib)
Starting Dose	1500 mg/m ² , 750 mg/m ² BID
-1 ^a	1100 mg/m ² , 550 mg/m ² BID
-2 ^a	750 mg/m ² , 375 mg/m ² BID

Abbreviation: BID: twice daily

^aSince capecitabine is provided as 150 mg or 500 mg tablets, it is recommended that the capecitabine dose reduction(s) (to 75% [level -1] or 50% [level -2] of the starting dose) is rounded down to the nearest 500 mg or multiple of 150 mg for the BID dose. If the patient's body surface area is >2.0, the standard of care for the study center can be utilized for capecitabine mg/m² dosing.

The recommended dose reduction for the -1 dose level of lapatinib is listed in [Table 4](#). Lapatinib doses should be held in patients with an LVEF that is Grade ≥ 2 and in patients with an LVEF that decreases below the institution's lower limit of normal (LLN; <50% if not specified). Lapatinib (in combination with capecitabine) may be restarted at a reduced dose of 1000 mg/day after a minimum of 2 weeks, if the LVEF recovers to normal and the patient is asymptomatic.

Lapatinib doses should be held in patients with Grade ≥ 2 NCI CTCAE toxicity, until the toxicity improves to Grade ≤ 1 ; lapatinib may be restarted at 1250 mg/day. If the toxicity recurs, then lapatinib (in combination with capecitabine) should be restarted at a reduced dose of 1000 mg/day.

Table 4. Dose Reduction Levels for Lapatinib-Related Toxicity

Dose Level	Lapatinib
Starting Dose	1250 mg
-1	1000 mg (750 mg for severe hepatic impairment; see Appendix 2)

Recommended dose reductions for the -1 and -2 dose levels of capecitabine in combination with lapatinib are listed in [Table 5](#).

Table 5. Dose Reduction Levels for Capecitabine-Related Toxicity (When Administered in Combination with Lapatinib)

Dose Level	Capecitabine (administered in combination with lapatinib)
Starting Dose	2000 mg/m ² , 1000 mg/m ² BID
-1	1500 mg/m ² , 750 mg/m ² BID
-2	1000 mg/m ² , 500 mg/m ² BID

Abbreviation: BID: twice daily

If doses of investigational product are held, study procedures for that cycle will proceed on schedule as planned, without any delay. This also applies to tumor assessments, which should continue to be done every 6 weeks, starting from the first dose of investigational product until the first planned tumor assessment at 6 weeks (± 3 days), and then after every subsequent 6 weeks (± 3 days) of treatment regardless of any changes in dose or occurrence of AEs. Missed dose(s) of investigational product (i.e., any dose that is not administered within the protocol-defined administration window) will not be made up. The dose adjustment guidelines represent the minimum set of measures that Investigators must follow. However, additional measures may be taken, as necessary, for certain patients per the Investigator's medical judgment. All dose modifications/adjustments should be documented in the patient's source file.

Once an investigational product dose has been reduced for a patient, all subsequent cycles must be administered at that dose, unless further dose reduction is required. Dose re-escalation is not permitted.

Patients must discontinue an investigational product if a criterion for investigational product withdrawal is met (see Section 10.1 and Appendix 2).

Once an investigational product has been discontinued, patients who had been receiving combination therapy may continue to receive the other investigational product as monotherapy, at the Investigator's discretion. This is applicable to both treatment arms of the study. Reintroduction of the discontinued investigational product at a later time during the active treatment phase is not permitted.

Detailed rules for dose adjustments of neratinib, lapatinib, and capecitabine in case of toxicity are provided in Appendix 2.

6.2 Packaging, Labeling and Storage

Detailed packaging information for all investigational products is available in a study reference manual(s). All investigational products will be labeled according to local regulations.

The Sponsor will supply all investigational products (as required), which should be stored at the study sites in a secure location with limited access.

All investigational products should be stored at 25°C (77°F) or below; do not freeze. Excursions are permitted to 30°C (86°F). Neratinib should be stored with desiccant. Keep containers closed tightly.

6.3 Drug Accountability

The study site must maintain accurate records documenting dates and quantities of investigational product received from the Sponsor. On a per patient basis, records must be maintained documenting dates and quantities of investigational product dispensed and returned at each study visit. Any investigational product accidentally or deliberately destroyed must be documented.

Throughout the study, reconciliation will be made between the amount of investigational product supplied, dispensed, returned, and subsequently destroyed or returned to Sponsor. All investigational products that were supplied by the Sponsor will be returned to Sponsor or its representative, or destroyed at the site in accordance with Sponsor guidelines.

Individual patient dosing compliance should be reviewed at each study visit by study site staff. If patient non-compliance is noted, the patient should be re-instructed regarding proper dosing procedures in order to continue in the study. If repeated non-compliance is noted, additional steps may be taken, including withdrawal of the patient from the study (see Section 10.2).

7 CONCOMITANT TREATMENT

All concomitant treatments, therapies and medications will be captured from the signing of the ICF until the end of the treatment. This will include the start date, stop date, generic name, route of administration, dose and indication for treatment.

At screening, patients will be asked what medications they have taken during the last 30 days, which medications are ongoing at the time of screening, any medical conditions that require medication, and all prior cancer therapies. At each subsequent study visit, patients will be asked what concomitant medications they are currently taking.

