9.4 Safety Follow-up Contact

Patients will be contacted by phone 28 days (+5 days) after the last dose of investigational product to collect AE, cancer therapy (anti-cancer medication, cancer-related radiotherapy, and cancer-related surgery), concomitant medication, and survival information.

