9.5 Long-term Follow-up Phase

Patients who discontinue study therapy will be followed for survival status during the long-term follow-up phase. If a patient discontinued study therapy due to toxicity, tumor assessments will continue to be performed at 6-week intervals throughout the long-term follow-up phase, until documented disease progression, death, or withdrawal of consent. Patients will also be contacted every 12 weeks for survival status and to collect the following data:

- Anti-cancer medications, including dose and regimen, taken since last contact.
- Cancer-related radiotherapy administered since last contact.
- Cancer-related surgeries/procedures performed since last contact.

The long-term follow-up phase will continue until patient death or withdrawal of consent. Survival follow-up will occur via telephone call if the site is unable to confirm status via chart review.

If a patient withdraws from the long-term follow-up phase of the study, attempts should be made to contact the patient to determine the reason(s) for discontinuation (see Section 10.3).

Patients who are no longer continuing with scheduled study visits will be followed for SAEs until the patient starts a subsequent cancer therapy (see Section 13.3).

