8.2.3. Central Nervous System Disease (CNS)

Time to intervention for symptomatic metastatic central nervous system disease is defined as the time from randomization to the first start date of an intervention for symptomatic metastatic CNS disease. Subjects that do not have an intervention for symptomatic metastatic CNS and do not die will be censored at the last date known alive on or prior to the data cutoff. Deaths are treated as competing events. Interventions for symptomatic CNS disease will include anti-cancer medication, cancer-related radiation therapy, cancer-related surgery/procedure, or concomitant medication/therapy as collected on the CNS CRF.

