3.1. Secondary CNS endpoint

The secondary CNS endpoint is time to intervention for symptomatic CNS disease. This is defined as the time from the date of randomization to the first date of an intervention for symptomatic metastatic CNS disease. Interventions include medications to control signs or symptoms caused by the CNS metastases (ie, high dose steroids in case of cranial hypertension), CNS radiotherapy, CNS surgery and cancer treatment specific for CNS metastases.

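### The tested CNS endpoint counts symptom-control medication until last date known alive, but no listed visit after the 28-day safety contact asks for it

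*Protocol*

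**What the plan says.** **What counts as an event.** SAP 8.2.3 lists four kinds of intervention: anti-cancer medication, radiation, surgery or procedure, and "concomitant medication/therapy as collected on the CNS CRF". Supplemental SAP 3.1 is more specific: "Interventions include medications to control signs or symptoms caused by the CNS metastases", with high-dose steroids as its example.

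**How long patients are at risk.** Under SAP 8.2.3 a patient with no intervention who has not died is censored at the last date known alive up to the data cutoff. Death is a competing event. Risk time therefore continues through long-term follow-up.

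**What is collected, and until when.**
- Protocol section 7: concomitant treatments "will be captured from the signing of the ICF until the end of the treatment".
- Protocol 9.4, the telephone contact 28 days (+5) after the last dose: the list of items ends with "cancer-related surgery), concomitant medication, and survival information". The Appendix 1 schedule agrees. This is later than section 7 allows.
- Protocol 9.5, every 12 weeks afterwards, besides survival status: "Anti-cancer medications, including dose and regimen, taken since last contact"; "Cancer-related radiotherapy administered since last contact"; "Cancer-related surgeries/procedures performed since last contact". Appendix 1 note k repeats these three items. The concomitant-therapy row of the schedule has no entry for long-term follow-up.
- The CNS CRF appears in neither 9.5 nor Appendix 1, and neither document says when it is completed.

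**Role of the endpoint.** SAP 8.3 tests it after PFS and OS, at 0.04 or 0.05. All other secondary endpoints are descriptive.

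**The concern.** The event definition and the follow-up list do not match. Of the four intervention types, three are requested for as long as the patient is followed. The fourth, medication given to control symptoms of CNS metastases, is not requested after the 28-day contact. A supportive steroid is not an anti-cancer medication, radiotherapy or surgery, so a site working from the visit list has no prompt to report it. The patient nevertheless continues to contribute time at risk.

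Two things are at stake. First, the endpoint may lose events, or date them late when radiotherapy or surgery follows the medication. Second, medication-only events are looked for over a longer period in whichever arm stays on treatment longer. If neratinib delays progression, that makes its CNS event rate look slightly higher relative to control.

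**Working it through.** **Inputs from the documents**
- Average durations (Protocol 4.1, SAP 2.2): screening 0.5, treatment 9.5, long-term follow-up 18 months. Check: 0.5 + 9.5 + 18 = 28, the stated average participation.
- Planning medians (Protocol 12.7, SAP 2.6): PFS 8.0 and 5.6 months; OS 30.3 and 22.0 months (neratinib, lapatinib).

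**Assumptions not in the documents**
- m, the share of first CNS interventions that are symptom-control medication only: 10%, 30% or 50%.
- A constant CNS hazard, 0.5 to 1% per month in the simulation.
- PFS as a proxy for time on treatment.
- The CNS CRF captures no medication-only event after the 28-day contact. This is the point the documents leave open.

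**Step 1: exposed share of risk time.** Risk time after randomization averages 9.5 + 18 = 27.5 months. The 28-day contact extends collection by 28/30.4375 = 0.92 months.
- Section 7 read alone: 18/27.5 = 65%.
- With the 28-day contact: (18 − 0.92)/27.5 = 17.08/27.5 = 62%.

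**Step 2: events lost.** Only medication-only events are exposed, so the share of all events lost is m × 0.621:
- m = 10%: 0.062, or 6%
- m = 30%: 0.186, or 19%
- m = 50%: 0.311, or 31%

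For each m this is an upper value under the average durations, because an event followed by radiotherapy or surgery is dated late rather than lost.

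**Step 3: difference between arms, crude rates.** Take exponential times with the planning medians, capped at 50 months.

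| | Neratinib | Lapatinib |
|---|---|---|
| Mean time on treatment (months) | (8.0/ln 2)(1 − 2^(−50/8.0)) = 11.39 | (5.6/ln 2)(1 − 2^(−50/5.6)) = 8.06 |
| Mean time at risk (months) | (30.3/ln 2)(1 − 2^(−50/30.3)) = 29.79 | (22.0/ln 2)(1 − 2^(−50/22.0)) = 25.17 |
| Exposed share | 1 − (11.39 + 0.92)/29.79 = 0.587 | 1 − (8.06 + 0.92)/25.17 = 0.643 |

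With no true effect, the observed rate ratio is (1 − 0.587m)/(1 − 0.643m):
- m = 10%: 0.9413/0.9357 = 1.01
- m = 30%: 0.8239/0.8071 = 1.02
- m = 50%: 0.7065/0.6785 = 1.04

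**Step 4: difference between arms, Cox model.** The crude ratio understates the effect. The neratinib arm's longer survival adds late off-treatment time, which narrows the gap between the averages. A Cox model compares the arms at equal follow-up time. Simulations with the same medians and a month-50 cut-off, varying accrual and the link between treatment time and survival, gave these cause-specific hazard ratios:

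| m | Events lost | True HR 1.00 reads | True HR 0.70 reads |
|---|---|---|---|
| 10% | 6–7% | about 1.01 | about 0.71 |
| 30% | 17–20% | about 1.04 | about 0.73 |
| 50% | 27–34% | 1.06–1.08 | 0.75–0.76 |

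These describe the cause-specific hazard ratio. The effect on Gray's test, which the SAP plans for this endpoint, was not calculated.

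**The case against.** The strongest reply is that section 7 governs the general medication log, while SAP 8.2.3 takes the endpoint from a dedicated CNS CRF. The end of the general log does not show that the CNS form ends too, and its completion instructions are not among the documents. This stands, and it means loss of events is not demonstrated. But the form is not scheduled at any visit after treatment, and the follow-up list that is written out omits one of the event types the form is meant to hold.

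A reader might infer more than the documents support, in three ways:
- *That medication collection stops at the end of treatment.* Section 7 alone says so; section 9.4 and Appendix 1 add the 28-day contact.
- *That CNS events in general are missed in proportion to time off treatment.* Anti-cancer drugs, radiotherapy and surgery or procedures are requested every 12 weeks until death or withdrawal of consent. Only medication-only interventions are exposed.
- *That the treatment comparison is materially biased.* At a 10% share the distortion is about 0.01 on the hazard ratio. It reaches 0.04 to 0.08 only if half of first interventions are medication only, and it runs against the arm treated longer, so it would not manufacture a neratinib benefit.

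The Supplement also plans partial checks. Section 3.3.1 analyses time to first CNS radiation, which is collected throughout; this is largely protected, although other CNS treatments are competing events there and could themselves go unrecorded. Section 3.3.2 analyses progressive CNS lesions from tumour assessments, but does not count events after new anti-cancer therapy starts, so it says little about much of the period in question.

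Finally, the endpoint is tested only if OS is significant, and no power is stated for it. That limits the consequence without removing the mismatch.

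**Conclusion.** The point holds in a limited form. The documents show that a type of event the endpoint counts is not on the collection list after the 28-day contact, which leaves about 62% of average risk time exposed. They do not show that events are actually lost, because the schedule of the CNS CRF is not stated.

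If sites follow the listed visits and the form adds nothing, the loss under the plan's average durations is at most about 6%, 19% or 31% of events for assumed medication-only shares of 10%, 30% or 50%. The distortion of a null hazard ratio ranges from about 1.01 to between 1.04 and 1.08, depending on that share and on the method. The main harm is lost or late-dated events; the imbalance between arms is secondary.

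The change is worth making because this is the only secondary endpoint with controlled alpha, and because it alters what sites are asked to collect rather than only recording a policy.

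**What to change.** 1. Add an item to Protocol 9.5 and to Appendix 1 note k: at each 12-weekly contact, sites record on the CNS CRF any intervention for symptomatic CNS metastases, including symptom-control medication, with its start date.
2. Reconcile Protocol sections 7 and 9.4 on when collection of concomitant medication ends.

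The cost is one question at an existing contact and a prompt on the CRF, with slight extra work for sites. Treatment, sample size and analysis method are unchanged.
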